To determine the effect of patient race in moderating the effect of 12 months of exposure to CHAMPION on the clozapine prescribing practices of prescribers and objectively measured medication persistence of their patients prescribed clozapine. We will also examine the impact of site and participant characteristics as well as attendance on outcomes.

In summary, if demonstrated to be efficacious, CHAMPION will have significant public impact by increasing the use of clozapine. This project addresses key NIMH priorities including improving access to evidence-based practices, focusing on disparities, and including innovative technologies. This project features a novel intervention, a renowned team of experts and the support of local and national organizations positioned to ensure its success.

PARTICPANTS AND RECRUITMENT AND RETENTION PLAN

Participants and Recruitment and Referral Sources

We will complete all recruitment and enrollment prior to initiation of the intervention. We will enroll 300 prescribers (physicians, nurse practitioners, physician assistants or other doctoral level providers approved to prescribe clozapine in the State of Maryland) as well as other team members at the sites (up to 300). We will recruit prescribers/clinical team from State of Maryland Outpatient Mental Health Centers (OMHC) and other clinical sites. We plan to attempt to enroll approximately 2 OMHCs by county; overall, we plan to enroll approximately 60 sites (approximately 5 prescribers/clinical team per site) with 30 in the CHAMPION group and 30 in the enhanced treatment as usual (TAU) group with N=150 prescribers per group. We may have a few more or less sites to reach the 300 prescriber target for the primary outcome and up to 600 total. We will allow individual prescribers to enroll if they are not affiliated with an enrolled study site, however they will not receive the ANC Point of Care Device, laptop computer, or site stipend. They are eligible for the individual compensation and education benefits if applicable.

Inclusion and Exclusion Criteria

Sites that enroll will have approximately 5 prescribers per site. Other members at the site can enroll. The specific inclusion/exclusion criteria for prescribers includes:

- 1) Located at a site in the State of Maryland with at least 3 prescribers at the site.
- 2) Prescribers/clinical team should be licensed in the State of Maryland and have prescribed antipsychotics previously.

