Analysis of Secondary and Exploratory aims.														
Archive ECHO lectures for website at end of 12 months														
Period of Medicaid Data Collection 2 (Aim 1)														
Post Testing on Knowledge and Self-Reported Competence (Aim 2)														
Meetings with NASHMPD														
Analysis of Project ECHO Post data														
Make videotaped ECHOs available to all participants once 12-month Medicaid data completed.														
National Webinar with NASHMPD and APA CSS SMI														
Submit symposium abstract to national														

CHAMPION PROTOCOL

meetings, e.g. IPS, SIRS														
Data Repository Submission														

STATISTICAL DESIGN AND POWER

Primary Outcomes

Specific Aim 1: The primary outcome examines Maryland Medicaid (and HMIS for inpatient) prescription data, which will be used to assess the increase in the proportion of patients treated with clozapine for those in the care of prescribers/clinical team randomized to the CHAMPION relative to the ETAU condition. We will also examine persistence in the use of clozapine for patients who are prescribed clozapine under the care of prescribers/clinical team randomized to CHAMPION compared to prescribers/clinical team randomized to the ETAU. The specific outcome assessments using Medicaid data include:

a. Proportion of clozapine prescriptions: Clozapine prescribing rates will be calculated from Medicaid prescription data. National Prescriber Identification (NPI) numbers will be used to identify the antipsychotic prescription records for each prescriber in the study. The denominator will be the number of unique individuals with a diagnosis of schizophrenia who had at least 1 prescription for an antipsychotic during each time period (12 months prior to start of study, during active study participation, and 12 months after the intervention period ends). For each individual in the sample, an indicator will be created that reflects whether the person had any prescription for clozapine during each of the time periods.

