to using a standard Likert scale for self-reported competence evaluation (2). Self-efficacy ratings of competence have been shown to be increased in a mental health ECHO model (6); are recommended as a measure for approaching measurement of practice outcomes (7); and, when using VAS to measure self-efficacy competence, have been found to be a reliable and valid measure for this construct (8-10).

b. Knowledge: We will use multiple-choice questions (MCQ) to assess knowledge. The knowledge-based test questions will consist of 52 questions that will cover 2 questions per 26 topic areas and will conform to best practices and guidelines for design of the questions (11). MCQ have been used to assess knowledge with ECHO models (6, 12) and are known to be a reliable and valid measure for measuring knowledge (11). The total score will range from 0-52 correct answers.

Power

Hypothesis 1: Considering the intent to treat (ITT) approach to analyses, we will be able to assess administrative data prescription records for all prescriber participants regardless of their level of participation in the CHAMPION intervention sessions or other research data collections efforts. Missing data will be a concern only for those time periods where prescriber participants were not practicing in the Maryland public health system (before or after the intervention time period). We assume that we will have administrative data records from at least 85% of the prescribers/clinical team across all time points. We calculated the needed sample size using PASS version 13 (13) for independent proportions in a clustered-randomized design with the following specifications: alpha-level = .05, power = .80, effect size (h) = .39 (small to medium) and ICC = .01 (prescribers/clinical team nested within site). Effect size is based on estimating an 11% improvement in the rate of clozapine prescribing in CHAMPION; e.g. a 4% rate of clozapine prescribing in the ETAU group and a 15% rate in the CHAMPION condition. The required sample size is 254 based on clusters of 4-5 prescribers/clinical team per site.

Hypothesis 2: Even with a conservative estimate of the number of patients per prescriber on clozapine, a high ICC (.20) for patients nested within prescriber, and a small effect (d = .3), the power to detect differences in clozapine persistence between conditions is greater than 95%.

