Hypothesis 3: Although the variables for hypothesis 3 are normally distributed, the specifications are the same and the power calculations are identical to those noted above. Based on literature described in Approach section 10 above, we anticipate changes in knowledge and competence to be large ($>.8$).

Hypothesis 4: Using the values above and the SAS macro from O'Rourke and MacKinnon (14), the power to detect indirect effects (mediation) will be greater than .80 when using the bias corrected bootstrap procedure when paths a and b are at least 0.3 (small to medium effects anticipated).

Statistical Analyses Overview

All data will be screened for errors using frequency and contingency tables and univariate and bivariate plots before formal analysis. These informal plots and summaries will allow us to be cognizant of data distribution characteristics before building regression models. We anticipate that our dependent variables will either have a distribution that is relatively bell-shaped or can be transformed to be relatively bell-shaped. Site will be included in all models as a random effect. Prescriber is nested within intervention arm, by design, and will be specified as a random effect in all analyses that include patient level data. The intercept will be designated as random to account for the non-independence across time point when appropriate. SAS PROC MIXED or GLIMIX will be used for the analyses described below (15).

CHAMPION PROTOCOL

Missing Data

All analyses will be conducted within an ITT framework. As described above, missing data for hypotheses 1 and 2 will be limited due to the use of Medicaid prescription records for those outcomes. For hypotheses 3 and 4, we will compare the baseline characteristics of the prescribers/clinical team who drop out prior to completing the 12-month assessment to those prescribers/clinical team who do complete the assessment. If necessary, we will investigate how estimates/results change over a range of several plausible assumptions regarding the missing mechanism together with multiple imputations to most accurately capture existent random variability.

Multiple Comparisons

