To control for Type I errors, we will use the sequential Bonferroni-type procedure for dependent hypothesis tests of Benjamini and Hochberg (16) to control the false discovery rate at 5%. The false discovery rate is the expected (or on average) proportion of falsely rejected hypotheses. This procedure will be applied to the family of tests on the multiple associated measures corresponding to each aim. We will also control for if randomized to site or individual.

Analyses for Each Specific Aim and Hypothesis

Specific Aim 1: To determine the effect of 12 months of exposure to CHAMPION on the clozapine prescribing practices of prescriber participants and the objectively measured medication persistence of the patients prescribed clozapine.

Specific Aim 1, Hypothesis 1: *Relative to the prescribers/clinical team randomized to the ETAU condition (POC and consultation), prescribers/clinical team randomized to CHAMPION will significantly increase the proportion of patients in their care who are prescribed clozapine, as assessed using Maryland Medicaid prescription data.* Clozapine prescribing will be measured as the proportion of patients with any clozapine prescriptions (See Approach 5a). We will use a mixed-effects, 2-level model generalized linear mixed model (SAS Proc GLIMIX, log link) with percent adherence as the dependent variable and treatment group (CHAMPION/ETAU), time (pre-CHAMPION year (t=1), CHAMPION year (t=2), follow-up CHAMPION year (t=3), and time by treatment group as the independent variables of interest. However, since the main outcome will be calculated at t=3, a contrast statement, within the context of the full model, will be used to compare the two treatment conditions at t = 3, controlling for baseline, to test the primary hypothesis with a random site effect to account for intra-site correlation (ICC). The test of hypothesis 1 will operationally be the test of whether the coefficient of the CHAMPION/ETAU condition term is significantly >0 (two-sided test) at time t = 3. Post hoc analyses will use the same model to test effects at t = 2.

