Specific Aim 1, Hypothesis 2: *For patients who are prescribed clozapine, the patients of prescribers/clinical team randomized to CHAMPION will exhibit significantly greater persistence to clozapine treatment compared to patients of prescribers/clinical team randomized to the ETAU condition, as assessed using Maryland Medicaid prescription data.* Persistence (Approach Section 5b) will be measured as number of days of clozapine use. An episode will be identified as having begun during the 1 year prior to CHAMPION, during CHAMPION, or in the year after CHAMPION ends. A person can only have one episode in each of the time periods. We will use a generalized linear mixed-effects, 3-level model (SAS Proc GLIMIX, Poisson link), with a random site and a random prescriber effect to account for within site and within prescriber correlation (ICC). The longitudinal portion of the model will be treated as described for hypothesis 1. The test of hypothesis 2 will

CHAMPION PROTOCOL

operationally be the test of whether the coefficient of the CHAMPION/ETAU condition term is significantly greater than zero (two-sided test) at time 3. Post hoc analyses will use the same model to test for effects at time 2.

Specific Aim 2: To determine the effect of 12 months of exposure to the CHAMPION intervention on the knowledge and self-reported competence of prescribers/clinical team prescribing clozapine and how those mechanisms of change are associated with increased clozapine prescribing and persistence.

Specific Aim 2, Hypothesis 3: *Relative to the prescribers/clinical team randomized to the ETAU condition, prescribers/clinical team randomized to CHAMPION will demonstrate significantly increased levels of knowledge (correct number of MCQs) and self-reported competence (mean score on 0-100 mm VAS).*

Knowledge and competence are continuous measures that can be assumed to be normally distributed.

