Transformations will be used if necessary. They will be measured at two time points (baseline and end of the 1-year CHAMPION). A General Linear Mixed Model (Proc MIXED) will be used to estimate the effects of the two groups on change in knowledge and competence with site as a random effect. The test of hypothesis 3 will operationally be the test of whether the coefficient of the CHAMPION/ETAU condition term is significantly greater than zero (two-sided test) at the post CHAMPION time point controlling for baseline. In exploratory analyses, we will examine individual competence scores related to outcomes as above while controlling for multiple comparisons.

Specific Aim 2, Hypothesis 4: *Prescriber self-reported competence will mediate the effect of the CHAMPION on clozapine prescribing and persistence.* A separate model will be used for each outcome. The independent variable will be group assignment, the dependent variable will be rate of clozapine prescribing during the year following CHAMPION and the persistence of clozapine episodes, and the mediator will be the overall self-reported competence score (0-100 mm VAS) measured at 12 months, controlling for baseline. We will use the product of coefficients approach to test mediation. The rationale behind this method is that mediation depends on the extent to which the independent variable changes the mediator (i.e., path a), and the extent to which the mediator affects the outcome variable (i.e., path b). The PROCESS (17) macro for SAS will be used to generate 95% bias corrected confidence intervals for the relative indirect effects and other parameters.

Exploratory Analyses

We will examine the role of race in moderating the effects of CHAMPION. To determine whether there was differential benefit of the program for the AA patients, race and interaction terms (time by race) will be added to the models described above. Despite our previous work, it is possible that increases in prescribing will not occur similarly between AA and Caucasian patients, however, we will use data collected to adapt future iterations of the topics related to AA if we do not see similar improvements in prescribing. Specifically, we will examine the two competence questions related to AA and ascertain the relationship of these specific measures to prescribing for AA and Caucasian patients. We will also look at other variables by site and patient that may contribute to outcomes and will analyze the other clinicians and examine.

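### The race-moderation analysis adds race and time by race but no treatment-by-race term, so the prescribing and persistence models hold the CHAMPION ratio equal in both races

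*Combined protocol and SAP*

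**What the plan says.** The Exploratory Aims state the goal as moderation: "To determine the effect of patient race in moderating the effect of 12 months of exposure to CHAMPION on the clozapine prescribing practices", and likewise for persistence. The Exploratory Analyses section repeats the purpose, "To determine whether there was differential benefit of the program for the AA patients", and then gives the only model specification on the point: "race and interaction terms (time by race) will be added to the models described above".

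The models being extended are set out under Analyses for Each Specific Aim and Hypothesis. Hypothesis 1 uses a log-link mixed model with treatment group, time (t=1, 2, 3) and "time by treatment group as the independent variables of interest". The treatment contrast is read at t=3, controlling for baseline. For Hypothesis 2, "The longitudinal portion of the model will be treated as described for hypothesis 1".

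No section names treatment by race, treatment by time by race, or a CHAMPION/ETAU contrast computed separately by race.

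**The concern.** A moderation question asks whether the treatment contrast differs between groups, so the model needs a term that lets it differ. Time by race does not do this. It describes a race difference in change over time that both arms share. Two errors follow:

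- A background trend that differs by race and has nothing to do with CHAMPION can be read as differential benefit.
- A real race difference in the CHAMPION effect can be diluted or missed.

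The Exploratory Analyses section says the data will inform later versions of the AA-related topics if prescribing does not improve similarly in the two groups. A result meant for that use should come from a model that can show the difference.

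**Working it through.** **The plan's own figures.** The documents give no sample size, power or alpha for the race analysis, so there is no figure to reproduce. The check concerns model terms. The illustrations borrow only the planning rates in the Power section: "a 4% rate of clozapine prescribing in the ETAU group and a 15% rate in the CHAMPION condition".

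**Algebra.** Let a = 1 for CHAMPION and 0 for ETAU, r = 1 for AA and 0 for Caucasian, and t = 1, 2, 3. The model as written, on the log scale, is

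log μ = β0 + βA·a + βT(t) + βAT(t)·a + βR·r + βRT(t)·r

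The treatment contrast at time t (a = 1 minus a = 0) is βA + βAT(t). It does not contain r, so the AA-minus-Caucasian difference in the contrast is exactly zero, both at t=3 and for the change from t=1 to t=3. The parameter count agrees: 1 + 1 + 2 + 2 + 1 + 2 = 9 free parameters for 2 × 3 × 2 = 12 cells. Random site and prescriber intercepts add no treatment-by-race term.

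Adding βAR·a·r alone (10 parameters) frees the raw t=3 contrast, but the change from baseline still cannot differ by race. Adding βATR(t)·a·r as well (12 parameters) frees both. The race difference at t=3 is then βAR + βATR(3), and relative to t=1 it is βATR(3).

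**Illustrations.** Assumptions: 4% in every cell at t=1, equal cell sizes, no random effects, and only t=1 and t=3 fitted. In cases 1 to 3 the t=3 rates average over race to 4% under ETAU and 15% under CHAMPION; case 4 does not keep the 15% average. A log-Poisson fit of the written terms reproduces the race totals and the arm totals at each time. Because baselines are equal,

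- time by race = ln(AA total at t=3 / Caucasian total at t=3)
- common CHAMPION ratio = CHAMPION total at t=3 / ETAU total at t=3
- true three-way term = ln(AA ratio / Caucasian ratio)

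| Case | AA, ETAU vs CHAMPION (ratio) | Caucasian, ETAU vs CHAMPION (ratio) | Race totals at t=3 | Time by race, Poisson / binomial | Common ratio (Poisson) | True three-way term |
|---|---|---|---|---|---|---|
| 1 | 6% vs 13% (2.17) | 2% vs 17% (8.50) | 19, 19 | 0.000 / −0.025 | 30/8 = 3.75 | ln(2.167/8.5) = −1.367 |
| 2 | 5% vs 14% (2.80) | 3% vs 16% (5.33) | 19, 19 | 0.000 / −0.012 | 30/8 = 3.75 | ln(2.8/5.333) = −0.644 |
| 3 | 4.8% vs 18% (3.75) | 3.2% vs 12% (3.75) | 22.8, 15.2 | 0.405 / 0.405 | 30/8 = 3.75 | 0.000 |
| 4 | 4% vs 4% (1.00) | 4% vs 15% (3.75) | 8, 19 | −0.87 / −0.88 | 19/8 = 2.375 | ln(1/3.75) = −1.322 |

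Cases 1 and 2 show moderation that the planned term does not register. Case 3 shows a time-by-race ratio of e^0.405 = 1.50 with no moderation on the ratio scale. In case 4 the written model assigns a ratio of 2.375 to both races, although the true values are 1.00 and 3.75. The full model recovers both.

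**Scale.** The equality is imposed on the link scale. In case 3 the absolute effects are 18 − 4.8 = 13.2 and 12 − 3.2 = 8.8 percentage points, so effects that are equal as ratios are unequal as differences.

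**Precision of the right term.** If a share s of patients is AA, patients are independent and rates are similar, the race-specific effects have variances V/s and V/(1−s), where V is the variance of the overall effect. Their difference has variance V/[s(1−s)]: 1/0.25 = 4.0 at 50:50, 1/0.21 = 4.8 at 30:70, and 1/0.16 = 6.3 at 20:80. The documents give no race split, so this range is assumed.

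**The case against.** The strongest reply is that this is loose drafting. The section opens by speaking of moderation, refers to interaction terms in the plural, and adds them to models whose key term is already time by treatment, so the authors may have meant more. That is possible. But the parenthesis names time by race and nothing else, and the plural also fits several time contrasts or several models. If more was intended, it still has to be written down.

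A second reply is that cases 1 and 2 were built to cancel: ETAU prescribing moves in opposite directions by race and the race totals at t=3 come out equal. That is correct, and nothing in the documents suggests such a pattern. With ETAU flat at 4% in both races, CHAMPION rates of 10% (AA) and 20% (Caucasian) give time by race of ln(14/24) = −0.54 against a true three-way term of ln(2.5/5) = −0.69. Rates of 12% and 18% give ln(16/22) = −0.32 against ln(3/4.5) = −0.41. So the planned term is not always blind. It remains non-specific, because a shared background trend gives the same kind of signal.

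Three narrower points also stand:

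- For Hypothesis 2 the plan names a Poisson link; reading that as a log link is an assumption.
- The plan also relates two AA-specific competence questions to prescribing by race. That informs topic revision but does not compare the arms by race.
- The analysis is exploratory, with no stated alpha or power.

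**Conclusion.** The concern holds. The stated analysis cannot answer its own question at any sample size, because the named terms make the race difference in the CHAMPION effect zero by construction on the link scale. This follows from the model terms and not from the illustrative rates. The rates show only how far the planned term can mislead: about zero when the true ratio of ratios is 2.167/8.5 = 0.25 in a constructed worst case, and 1.50 when it is 1.00. In simpler patterns the planned term moves with the moderation but cannot be told apart from a trend common to both arms. The primary Hypothesis 1 test is not affected. The change should be made before the race analysis is run.

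**What to change.** In the Hypothesis 1 and 2 models only, since patient race has no meaning for the prescriber outcomes of Hypothesis 3:

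- Add treatment by race and treatment by time by race, with all lower-order terms.
- Name as the moderation test the race difference in the CHAMPION–ETAU contrast at t=3 relative to t=1, and state that on the log link it is a ratio of ratios.
- Report race-specific CHAMPION effects at t=3 with confidence intervals, and for prescribing also as absolute differences.
- Keep the exploratory label.

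For Hypothesis 1 the race analysis must use patient-level or race-stratified data, because a prescriber-level proportion cannot carry patient race. The patient-level outcome is already defined under Primary Outcomes ("an indicator will be created that reflects whether the person had any prescription for clozapine during each of the time periods"). The Statistical Analyses Overview already includes site as a random effect in every model, and says the prescriber effect "will be specified as a random effect in all analyses that include patient level data".

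The cost is a short model specification. Race is already among the requested Medicaid and HMIS variables. The HMIS table shows no Eastern Shore counterpart for race, which may be an extraction gap, and the Gladstone variables are not listed, so availability from those two sources should be confirmed. The three-way estimate will be imprecise, with 4.0 to 6.3 times the variance of the overall effect under the assumptions above. It should be read from its interval, and a non-significant result should not be taken as evidence of equal benefit.
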